Among AF patients with guideline indications for OAC for stroke prevention who have not received any OAC dispensing for at least one year, an education intervention at the patient-level and the provider-level will increase the proportion of patients started on OAC for stroke prevention.

IV. STUDY RATIONALE

Preliminary data from three Sentinel Data Partners between 1/1/2006 and 6/30/2015, identified 231,696 patients (1.4%) with at least 2 diagnoses of AF (ICD-9 codes of 427.31 or 427.32) over the study period, among 16.2 million covered lives. Within the 231,696 AF patients, there were 201,882 with a CHA₂DS₂-VASc score of 2 or greater (based on administrative claims data in the Sentinel Distributed Database), which is an American Heart Association (AHA)/American College of Cardiology (ACC) guideline indication for OAC. Over the study period from 2006 through 2015, 52% (n=105,256) patients filled at least one prescription for anticoagulation, meaning that 48% of patients with CHA₂DS₂-VASc score of 2 or greater never had a pharmacy claim submitted for an OAC during the study period. While there may be clinical or health system related reasons for not treating some of these patients, this apparent significant gap of guideline-based adherence is a public health issue of interest. The presented protocol is an opportunity to test the potential for developing and testing a health plan (Data Partner) based education intervention to improve the quality of care.

V. STUDY OBJECTIVES

A. PRIMARY OBJECTIVE

The primary objective is to evaluate the effect of the patient and provider education interventions (versus usual care with delayed provider education intervention) on the proportion of patients with evidence of at least one OAC prescription fill (defined as one OAC dispensing or 4 INR tests) over the course of the follow-up through the date on which at least 80% of eligible study participants have at least 12 months of follow-up time.

B. SECONDARY OBJECTIVE

The secondary objectives are to evaluate the impact on outcomes of the patient and provider education interventions over the course of the follow-up through the date on which at least 80% of eligible study participants have at least 12 months of follow-up time:

- 1. Incident rate of stroke or transient ischemic attack (TIA) hospitalization
- 2. Incident rate of hospitalization for stroke
- 3. Time to first OAC prescription fill
- 4. Proportion of days covered by OAC prescription fills

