A schematic diagram below shows the design of the delayed intervention portion of the study:

*All possible person-time will be used to assess participants' outcomes (patients will have different duration of follow-up).

For analysis, treatment status is at time of randomization or corresponding early intervention mailing; for the delayed intervention mailing it is prior to mailing.

VII. STUDY POPULATION

All inclusion and exclusion criteria will be determined by claims data. For entry into the study, the following criteria will be met:

A. INCLUSION CRITERIA

- 1. Two or more diagnoses of AF (ICD-9 and/or ICD-10 codes) at least one day apart and with at least one diagnosis within the last 12 months prior to the last date in the current approved data used for cohort identification
- 2. CHA₂DS₂-VASc score of 2 or greater
- 3. Medical and pharmacy insurance coverage of at least the prior year as identified via administrative claims databases of one of the participating Data Partners as of the date of randomization
- 4. Age 30 years or greater as of the last date in the current approved data used for cohort identification

B. EXCLUSION CRITERIA

- 1. Evidence of OAC medication fill (defined as 1 OAC dispensing or 4 INR tests) during the 12 months prior to randomization (determined at randomization for the early intervention cohort and 12 months post-randomization for the delayed intervention cohort)
- 2. Conditions other than AF that require anticoagulation, including treatment of deep venous thrombosis, pulmonary embolism, or ever having had a mechanical prosthetic heart valve prior to the last date in the current approved data used for cohort identification
- 3. Pregnancy within 6 months of the last date in the current approved data used for cohort identification
- 4. Any known history of intracranial hemorrhage prior to the last date in the current approved data used for cohort identification
- 5. Hospitalization for any bleeding within the last 6 months of the last date in the current approved data used for cohort identification
- 6. Patients with recent P2Y12 antagonist use (i.e. clopidogrel, prasugrel, ticlopidine, or ticagrelor within 90 days of the last date in the current approved data used for cohort identification

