- The sample size has 80% power to detect a 0.5% absolute reduction in stroke, assuming a cumulative 1-year incidence of stroke of 4.2% in control (delayed intervention arm) patients and 3.7% in intervention (early intervention arm) patients. The assumption is that patients not on oral anticoagulation have an annual stroke rate of 5%, and stroke will be reduced by 50% (HR=0.5) in the treated (anticoagulated) population. The 80% power requires that 52% of early intervention arm patients are treated at 1-year as compared to 33% in the control arm.

B. POPULATIONS FOR ANALYSIS

All analyses will be based on a modified intention-to-treat principle (i.e., all identified early intervention patients who meet eligibility and are mailed the intervention will be included; using "pseudo" wave assignments, all identified delayed intervention patients who meet eligibility at the time of corresponding early mailings will be included in the analysis). The primary endpoint will be calculated based on the proportion of patients with evidence of at least one OAC prescription fill over the course of the follow-up through the date on which at least 80% of eligible study participants have at least 12 months of follow-up time. An as-randomized analysis will be performed for the primary endpoint as a sensitivity analysis. All possible person-time will be used to assess participants' outcomes; patients will have different duration of follow-up and that will be accounted for in the analyses. Patients will be censored from the analysis at the time of death, disenrollment from the health plan, loss of medical or pharmacy coverage, or change in eligibility for inclusion in research based on health plan membership. The statistical analysis plan (SAP) provided more information and outlines in detail how granular aggregate data will be received from each Data Partner in lieu of patient-level data.

XV. OUTCOME DEFINITIONS

All outcome definitions will be based on available claims data.

- 1. Evidence of OAC start: the proportion of AF patients who have at least 4 INR values measured or who fill at least one OAC prescription for apixaban, dabigatran, edoxaban, rivaroxaban, or warfarin over the course of the follow-up through the date on which at least 80% of eligible study participants have at least 12 months of follow-up time

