6. Patients with recent P2Y12 antagonist use (i.e., clopidogrel, prasugrel, or ticagrelor within 90 days of prior to randomization)

F. STUDY DESIGN AND DURATION

As described in detail in the protocol, the study is a prospective, randomized, and open-label educational intervention trial. Patients with AF and a CHA₂DS₂-VASc score of 2 or greater were randomized in a 1:1 ratio to an early intervention cohort and a delayed intervention cohort within each participating health plan. The definition for OAC medication fill was an OAC medication dispensing or at least 4 INR tests in the claims data.³ The claims records of the patients randomized to the early intervention cohort were then linked to “fresh” (i.e., about 1 month old) pharmacy claims data at the time of randomization. Patients without evidence of an OAC medication fill during the 12 months prior to randomization were included in the patient-level and provider-level early educational intervention (patients randomized to this early intervention with evidence of an OAC medication fill during the 12 months prior to randomization were excluded from the trial). In addition to usual care, these patients and their providers received a one-time mailing at trial start. There were two waves of mailing for the early intervention cohort at most sites due to the practical challenges of claims data: the patients were assigned to wave 1 if they had a provider easily identified in the data (i.e., the provider associated with the most recent AF diagnosis is indeed an individual provider), and they were assigned to wave 2 if it was difficult to identify a provider (e.g., the first identified provider is actually a facility). Follow-up time started on the date of the respective wave 1 and wave 2 mailings for the early intervention patients.

The delayed intervention cohort will have received usual care over the initial study period. After the date on which at least 80% of all eligible study participants have at least 12 months of follow-up time, the treatment status of the delayed intervention group will be assessed via the Sentinel data available at that time, in addition to “fresh” pharmacy claims data. The providers of patients in the delayed cohort who did not receive OAC medication during the course of follow-up and still meet all inclusion criteria will receive the provider-only education intervention (patients will not receive the educational materials unless no provider can be identified for a mailing).

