[figure not shown]
Details on the analyses are provided in Section II. Here we describe the data sources for the **modified intention-to-treat** (primary) and **as-randomized** (sensitivity) analyses. Similar to early intervention cohort, the patients in the delayed intervention cohort will be assigned to wave 1 or wave 2 (“pseudo”

³Not all OAC dispensings are captured in pharmacy claims, particularly, for warfarin due to some patients paying for medication out of pocket. INR tests are assumed indicative of OAC fills that were not billed through the claims. Four INR tests or values within a 12-month period will be used as a proxy since that is roughly the number of tests administered in the process of stabilizing dose.

wave assignments) depending on the difficulty in identifying the patient's provider (the intent is to handle them the same way as was done for the early intervention arm, for the modified intention-to-treat analysis). The follow-up for the delayed intervention patients will start on the date the wave 1 or 2 mailings took place for a given Data Partner's early intervention cohort. For both early and delayed intervention cohorts, any patients who die, are disenrolled, or get started on OAC between the randomization and early intervention mailing will be excluded from the analysis at each Data Partner. For both the early and delayed arms, exclusion criteria that are based on member medical history were assessed at the time of randomization. For the early intervention cohort, enrollment and treatment status were assessed at randomization for all and re-assessed at the wave 2 time point at some of the sites (this was at site discretion, in response to the lag between wave 1 and 2 mailings). The enrollment and treatment status of the delayed intervention cohort will be examined for eligibility at the same time point as the early intervention patients, meaning at the time of mailing per Data Partner, via the locked data (using the wave 1 and 2 dates).

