Where $T = (p_{12}, p_{13}, \dots, p_{1k})'$, $p_{1k} = \Pr(\text{category } k \mid \text{early intervention})$, $k \in \{2, 3, \dots, k\}$,

$C = (p_{22}, p_{23}, \dots, p_{2k})'$, $p_{2k} = \Pr(\text{category } k \mid \text{delayed intervention})$, $k \in \{2, 3, \dots, k\}$,

S is a $(k - 1) \times (k - 1)$ covariance matrix define as:

$$S = [S_{kl}] = \begin{cases} \frac{[p_{1k}(1 - p_{1k}) + p_{2k}(1 - p_{2k})]}{2}, & k = l \\ \frac{[p_{1k}p_{1l} + p_{2k}p_{2l}]}{2}, & k \neq l \end{cases}$$

Aggregate standardized mean differences will be calculated based on aggregated frequencies, mean, and standard deviations.

Each Data Partner will run the SAS program(s) distributed by HPHCI, developed with the statistical team at Duke, to generate a summary table for their cohort of patients shown in example Tables 1 and 1S in Appendix A (there will be one for each Data Partner) and return the summary table to HPHCI. The same summary table will be generated for entire study population by HPHCI, as shown in Tables 1 and 1S in Appendix A.

As part of the provider intervention materials, providers had the opportunity to respond and provide an explanation for why their patients were not being treated with OAC. The data collected from these responses will be aggregated by rationale for non-treatment and reported as counts (percentages) by the coordinating center.

C. PRIMARY ENDPOINT DATA ANALYSES

The proportion of patients with evidence of at least one OAC medication fill over the course of the follow-up (through the date on which at least 80% of eligible study participants have at least 12 months of follow-up time) is the primary endpoint. The definition for OAC medication fill will be an OAC medication billing in the outpatient pharmacy claims, at least 4 INR tests or results in the laboratory claims (indicative of OAC use that was not billed through the pharmacy claims data), or a single procedure code that indicates use of anticoagulation. The primary endpoint will be summarized and compared between the early intervention and delayed intervention arms. Both unadjusted and adjusted

(based on available baseline risk factors) analyses will be conducted for the difference in the primary endpoint between the early intervention and delayed intervention arms using the data shown in Tables 2a-c. The adjusted analysis will be considered the primary analysis.

1. Adjusted Analysis Model

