The time to first OAC initiation, is defined by the first fill date for apixaban, dabigatran, edoxaban, rivaroxaban, or warfarin. If there was no prescription fill for these medications, but the patient had 4 or more INR tests or results documented over the study period, the date of the first INR measurement would be used for initiation of OAC. Cumulative incidence rates estimated using Kaplan-Meier product limit will be presented for early intervention and delayed intervention groups. A Cox proportional hazards¹¹ model with early intervention vs. delayed intervention as the main effect will be used to model the time to first OAC initiation, after adjusting for baseline risk factors listed in Appendix A Table A. Robust standard errors will be used to account for the correlation of responses among the patients from a same service provider. The proportional hazard assumption will be verified using cumulative sums of martingale residuals and the Kolmogorov-type Supremum test. The hazard ratio, 95% CI and p-value will be summarized for time to the endpoint. Each Data Partner will run the SAS program(s) distributed by HPHCI, developed with the statistical team at Duke DCC, to perform Cox regression model¹¹ on their cohort of patients and return the estimated hazard ratio, 95% CI and p-value, shown in Table 3 in Appendix A (there will be one for each Data Partner), to HPHCI. Meta-analysis methods with inverse-variance weighting on log scale will be used to integrate the results and obtain the overall estimate of the hazard ratio, 95% CI and p-value for the entire study population.

There are patients for whom a provider was not identified, and therefore the provider letters were not mailed out. The primary endpoint will be summarized using frequencies and percentages and compared using Chi-Square test between the patients with provider letter and the patients without provider letter among those in the early intervention group. Each Data Partner will return the descriptive data, shown in Table 4 in Appendix A to HPHCI. Similar summary table will be generated for entire intervention arm by HPHCI.

2. OAC Adherence

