History of peripheral vascular disease?					
N					
Yes, %					
History of prior cerebrovascular disease?					
N					
Yes, %					

	Overall (N=XXXX)	Early intervention (N=XXXX)	Delayed intervention (N=XXXX)	p-value	Stand. mean difference (%)
History of heart failure?					
N					
Yes, %					
History of kidney disease?					
N					
Yes, %					
History of MI					
N					
Yes, %					
History of CABG					
N					
Yes, %					
History of coronary stent					
N					
Yes, %					
CHA ₂ DS ₂ VASc score					
N					
Mean (SD)					
Median (25th, 75th)					
0, %					
1, %					
2, %					
3, %					
4, %					
5, %					
6, %					
7, %					
8, %					
9, %					
Bleeding risk score: ATRIA score					
Low (≤ 3), %					
Intermediate (4), %					
High (≥ 5), %					
Hospitalization in the prior 6 months					
0, %					
1, %					
2, %					
≥ 3 , %					
Mean (SD) follow up time					
Minimum follow up time					
Maximum follow up time					
Median follow up time (range across sites)					

For Tables 2 through 9: The SAP workplan(s) run at each Data Partner sites will generate Partner-specific tables of events (per outcome, for early vs delayed intervention) and unadjusted and adjusted model results. These will be returned to the coordinating center; results will be aggregated and meta-analyses will be run on site-specific models to generate final aggregated results.

Table 2a. Odds ratio of filling at least one OAC dispensing or 4 or more INRs (primary endpoint) over the course of the 12-months of follow-up: early intervention vs. delayed intervention in the modified intention to treat (mITT) analysis

	Early Intervention, n/N (%)	Delayed Intervention, n/N (%)	Unadj. Parameter Estimate (SE)	Unadj. Odd Ratio (95% CI)	Adj. Parameter Estimate (SE)	Adj. Odds Ratio (95% CI)	p-value for adjusted OR
OAC dispensing or ≥ 4 INRs at 365 days							
No. who met endpoint due to OAC							
No. who met endpoint due to 4 INRs							
No. who met endpoint due to other code							
No. who met due to 4 INR test PX codes (CPT)							

Table 2b. Odds ratio of filling at least one OAC dispensing or 4 or more INRs (primary endpoint) by varying windows of time (42, 90, and 183 days): early intervention vs. delayed intervention in the modified intention to treat (mITT) analysis

	Early Intervention, n/N (%)	Delayed Intervention, n/N (%)	Unadj. Parameter Estimate (SE)	Unadj. Odd Ratio (95% CI)	Adj. Parameter Estimate (SE)	Adj. Odds Ratio (95% CI)	p-value for adjusted OR

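### The SAP's primary endpoint adds a single unnamed procedure code that the protocol endpoint and the stated baseline OAC exclusion lack, so some existing users could be scored as starters

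*SAP*

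**What the plan says.** **Primary endpoint, SAP II.C.** There are three routes to an OAC fill: an outpatient pharmacy billing, at least 4 INR tests or results, "or a single procedure code that indicates use of anticoagulation". The Table 2a shell gives the third route its own line, "No. who met endpoint due to other code", apart from the lines for INRs and for INR test procedure codes. It is therefore a working route to an event and not another name for INR billing. Neither document names the code or says why it was added.

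**Primary endpoint, protocol.** There are two routes. Section V.A has "at least one OAC prescription fill (defined as one OAC dispensing or 4 INR tests" as the definition. Section XV, item 1, counts patients "who have at least 4 INR values measured or who fill at least one OAC prescription for apixaban, dabigatran, edoxaban, rivaroxaban, or warfarin". Section XVI.C gives the same two routes.

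**Baseline exclusion.** Protocol VII.B, criterion 1, reads "Evidence of OAC medication fill (defined as 1 OAC dispensing or 4 INR tests) during the 12 months prior to randomization". SAP I.F says: "The definition for OAC medication fill was an OAC medication dispensing or at least 4 INR tests in the claims data". SAP I.E uses the term OAC medication fill without listing routes, and refers to an external website for the complete code list.

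**Time to first OAC, SAP II.D.1.** The start date is the first fill. Without a fill, it is the first INR if "the patient had 4 or more INR tests or results documented over the study period". No date is given for a patient who qualifies only by the code, although the Table 3 shell has a line for events met by another code.

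**The concern.** The trial asks whether the letters cause untreated patients to start OAC. That needs the same evidence of use to be ruled out at baseline and looked for in follow-up. If follow-up accepts something that baseline ignores, a patient who was on OAC throughout can enter as untreated and leave as a starter.

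The SAP gives a reason why such patients exist. Footnote 3 in I.F says that some OAC use, warfarin in particular, is missing from pharmacy claims because some patients pay for it themselves. If they also have fewer than 4 billed INRs in the prior year, the stated exclusion does not find them. The 365-day washout in SAP II is specified only for the as-randomized sensitivity analysis, so it does not protect the primary modified intention-to-treat analysis.

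Two things are at stake. The headline result would rest on an endpoint that is not the protocol's. And events unrelated to the intervention would enter both arms, raising both rates and pulling the effect toward the null.

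**Working it through.** **1. Definitions side by side.**

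| Place | Dispensing | 4 INRs | Single procedure code |
|---|---|---|---|
| Protocol V.A, XV item 1, XVI.C (endpoint) | yes | yes | no |
| Protocol VII.B, criterion 1 (exclusion) | yes | yes | no |
| SAP I.F (definition used for eligibility) | yes | yes | no |
| SAP II.C (primary endpoint) | yes | yes | **yes** |
| SAP Table 2a, lines | yes | yes | **yes** |
| SAP Tables 2a–c and 3, titles | yes | yes | no |
| SAP II.D.1, text (time to OAC) | yes | yes | no date rule |
| SAP Table 3, lines | yes | yes | **yes** |

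The code enters on the endpoint side only.

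**2. The plan's own figure.** Inputs from SAP I.G.1 and Protocol XIV.A.1: 33% against 38%, two-sided 0.05, 1:1 allocation, continuity-corrected chi-square, 30% attrition. The test needs 1963, 2418 and 3401 per arm for 90%, 95% and 99% power. Dividing by 0.70 and rounding up gives 2805, 3455 and 4859, so the totals are 5610, 6910 and 9718. These match the table exactly. (They match only with the 30% allowance, although the protocol's caption says dropouts were not adjusted for. That is a separate matter.) The planned odds ratio is (0.38/0.62)/(0.33/0.67) = 1.244.

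**3. Effect of the mismatch.** Let q be the share of analysed patients in each arm who are existing users scored as starters only because of the code. Take the other patients to start at the planned rates. Then

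p′ = (1 − q)p + q, and the difference is (1 − q) × (0.38 − 0.33).

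For q = 5%: 0.95 × 0.33 + 0.05 = 0.3635 and 0.95 × 0.38 + 0.05 = 0.411. The odds ratio is (0.411/0.589)/(0.3635/0.6365) = 1.222.

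The documents give no q, so the range is an assumption:

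| q (assumed) | Delayed | Early | Difference, points | Odds ratio | Total N for 99% power, with 30% attrition |
|---|---|---|---|---|---|
| 0 | 33.0% | 38.0% | 5.00 | 1.244 | 9,718 |
| 1% | 33.7% | 38.6% | 4.95 | 1.240 | 9,992 |
| 5% | 36.4% | 41.1% | 4.75 | 1.222 | 11,150 |
| 10% | 39.7% | 44.2% | 4.50 | 1.203 | 12,740 |
| 20% | 46.4% | 50.4% | 4.00 | 1.174 | 16,518 |

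**4. Power.** With 80,000 enrolled and 30% attrition, 80,000 × 0.70 = 56,000 are analysed. Power is above 99.9% on every line of the table.

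**The case against.** **The programmed exclusion may already use the code.** The complete eligibility code list is on an external website. This stands as a limit. The documents show that the stated definitions omit the code; they do not show what was programmed. They also do not say that the code was applied at baseline.

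**The count will be visible.** Table 2a reports code-only events by arm. That is true and useful, but no odds ratio without those events is planned.

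**The size is assumed and modest.** This stands. Some existing users would also qualify in follow-up by 4 INRs or an insured fill. They would be misclassified under the protocol's definition too, and aligning the code does not help them.

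A reader might infer more than the documents support:

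- *That the primary and time-to-event analyses count different events.* Table 3 has a line for the other code, and its title calls the outcome the primary endpoint. II.D.1 lacks a date rule; that does not establish a different event set.
- *That the SAP allows a longer INR window than the protocol.* SAP footnote 3 says "Four INR tests or values within a 12-month period will be used as a proxy", the footnote in Protocol VI says nearly the same, and Table 2a is fixed at 365 days. No difference between the documents is shown.
- *That the code could create a false benefit.* This would need existing users in the early arm to receive the code more often. The letters do urge patients to see their provider, so it is conceivable. At an assumed q of 5%, a 10-point difference in capture would add 0.05 × 10 = 0.5 points. But the documents give nothing that shows or sizes such a difference.

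**Conclusion.** The mismatch is in the text. SAP II.C and Table 2a count a route that the protocol's endpoint and the stated baseline definitions do not have, and the route is left unnamed. Followed as written, the primary result would use an endpoint different from the protocol's and could score existing users as starters.

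The likely effect is dilution, to 5 × (1 − q) points. For an assumed q of 5% to 10% that is 4.75 to 4.5 points, or an odds ratio of 1.22 to 1.20 against 1.244, with no material loss of power. This rests on three assumptions: q is equal in both arms, the planned rates hold in everyone else, and the 33% rate refers to the two-route definition. The protocol does not say which definition its feasibility assessment used. The point concerns the validity and consistency of the endpoint. It does not threaten the trial's ability to detect the planned effect, and if the external code list already applies the code at baseline, only the departure from the protocol and the missing wording remain.

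**What to change.** Name the procedure code or codes in the SAP, and use one definition of OAC fill for the exclusion and the endpoint. Either alignment is valid:

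- **Option A.** Keep the protocol's two routes as the primary endpoint and report the code route as a sensitivity analysis. A few true starters seen only through the code then leave the primary count.
- **Option B.** Keep the code in the endpoint and apply it identically in both arms to the 12 months before follow-up starts. Use data refreshed at analysis for this look-back: SAP I.D says that the fresh linkage covers pharmacy claims and enrollment, while routine data are several months old, so the archive may miss codes shortly before mailing. A few more patients are then excluded at baseline. The protocol's endpoint text must be changed to match.

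In either case:

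- Report the adjusted odds ratio with and without code-only events.
- Add a date rule for the code to II.D.1, to match the line in Table 3.
- Align SAP I.F, II.C and the titles of Tables 2a–c and 3.
- State whether the external eligibility code list contains the code.

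The cost is SAP wording, one flag in the distributed program and one extra model per Data Partner. Option B also needs the look-back run on refreshed data.
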